### **3.3.2 Rationale for Patient Population**

Patients with congenital hemophilia A *who have persistent* inhibitors against FVIII at enrollment will comprise the primary population for this Phase IIIb study investigating the safety, *tolerability*, efficacy, immunogenicity, and PK of prophylactic administration of emicizumab.

Patients may have received episodic or prophylactic treatment before enrollment; at least one documented treatment with bypassing agents or FVIII concentrates is required within the last 6 months to indicate the need for prophylactic emicizumab treatment.

Based on current treatment algorithms for patients with hemophilia A with inhibitors (Kempton and White II 2009; Srivastava et al. 2013), it is anticipated that the majority of adults and adolescents treated with emicizumab will have previously undergone ITI without success or are not candidates for ITI. As clinical safety data relating to the concomitant use of prophylactic emicizumab during ITI are not available at this time, patients currently receiving ITI will not be eligible for this study. *Patients receiving ITI therapy will be eligible following the completion of a 72-hour washout period prior to the first emicizumab administration.* Owing to the fact that the presence or amount of FVIII inhibitors in their plasma does not impact the efficacy of emicizumab, patients' inhibitor titers at the time of study entry will not influence their study eligibility.

### **3.3.3 Rationale for Control Group**

This study involves the use of a single-arm study design and therefore a control group will not be used. The primary endpoint of this study is to evaluate the overall safety and tolerability of prophylactic administration of emicizumab in patients with *congenital hemophilia A who have persistent inhibitors against FVIII*. As hemophilia A is a rare disease (Acharya 2013) and the study is designed to investigate the broad safety profile of emicizumab, approximately 200 patients will be enrolled. Given the size of the patient population, a single-arm study design without a control group is considered an appropriate method to capture the safety data that will be observed following the use of emicizumab. This type of study design has been used extensively in previous clinical studies involving patients with rare diseases (Bell and Tudur Smith 2014).

### **3.3.4 Rationale for Biomarker Assessments**

The identity of effective PD, safety, and bone and joint biomarkers has not been fully elucidated and further testing is required to determine which assays and technical conditions are most suitable for use with emicizumab treatment. Plasma and serum samples will be collected for PD, safety, and bone and joint biomarker assessments at specific clinic visits in order to obtain evidence of the biologic activity of emicizumab in patients (see Appendix 2

Schedule of Biomarker Samples

).

The PD biomarkers include, but are not limited to, coagulation assays such as aPTT and FVIII activity assays. The results of the Phase I/II study have *shown* that a dose-response relationship was apparent between aPTT and emicizumab concentration (for more information, see the Investigator's Brochure). The aPTT assay will be run in a modified form to ensure that the assay range covers all levels of emicizumab exposure. In addition, clot waveform analysis (CWA) may be run as an exploratory PD coagulation assay.

The safety biomarkers will be used to monitor patient safety throughout the study and may include, but are not limited to, D-dimer.

Exploratory safety coagulation system biomarkers will include Factor VIII antigen (FVIII:Ag), Factor IX antigen (FIX:Ag), and Factor X antigen (FX:Ag) to assess whether drug treatment causes alterations in the circulating levels of the coagulation factors that are the binding targets for emicizumab. Measurement of other coagulation or hemophilia-related factors may also be conducted.

The bone and joint biomarkers will include exploratory biomarkers of bone turnover and joint health. The selection of bone and joint biomarkers that will be tested will be based on findings from biomarker analyses in other emicizumab trials (see Appendix 2

Schedule of Biomarker Samples

).

Residual blood and/or, plasma, and serum from collected *biomarker* samples may be stored for *up to 5 years* after the *final Clinical Study Report has been completed* and may be used for additional exploratory emicizumab-related research, to guide development of potential *in*

*in vitro* diagnostic assay(s) related to emicizumab plasma concentration, FVIII inhibitor titre and/or coagulation activity.

### **3.3.5 Rationale for Pharmacokinetic Sample Collection Schedule**

PK samples will be collected throughout the *2-year study period* in order to further investigate the PK of emicizumab (see the Schedule of Activities; [Appendix 1](#) Schedule of Activities ).

### **3.3.6 Rationale for Immunogenicity Sample Collection**

Immunogenicity will be monitored by investigating the incidence and clinical significance of antibodies to emicizumab at specified time points (see the Schedule of Activities; [Appendix 1](#) Schedule of Activities

). The emergence of *anti-drug antibodies* (ADAs) has been previously observed in clinical studies involving monoclonal antibodies of the IgG4 class ([Lundkvist et al. 2012](#); [Vennegoor et al. 2013](#)).

### **3.3.7 Rationale for Disease Response–based Endpoints**

The secondary objective of this study is to evaluate the efficacy of prophylactic administration of emicizumab. This objective will be achieved by investigating the number of bleeds over time under emicizumab treatment, *assessing HRQoL, and evaluating health status according to EQ-5D-5L and patient preference for the emicizumab regimen compared with the previous regimen*. As mentioned in [Section 0](#), this analysis will occur when all patients have completed 2 years of treatment or have withdrawn, whichever occurs sooner. In order to obtain comprehensive data on each bleed, patients will be asked to report bleed information *on an ePRO device where possible*, including site of bleed, type of bleed, time of each individual bleed (day, start and stop time), and treatment for bleed.

Conducting the efficacy analysis after 2 years of therapy is supported by the results of previous clinical studies that have demonstrated the benefits of long-term prophylactic therapy in patients with hemophilia ([Gringeri et al. 2011](#); [Khawaji et al. 2012](#); [Manco-Johnson et al. 2007](#)). The results of these studies showed that prophylactic treatment could effectively prevent joint damage, decrease the frequency of joint and other hemorrhages, and lead to improvements in the patients' HRQoL.

### **3.3.8 Rationale for Primary Endpoint Selection**

As stated in [Section 0](#), the primary objective of this study is to evaluate the overall safety and tolerability of prophylactic administration of emicizumab. In order to achieve this objective, *the incidence and severity of all adverse events, including adverse events of special interest, will be captured on an ongoing basis, as they occur during the study*. Physical examinations, vital signs, and laboratory values will be assessed as per the Schedule of Activities ([Appendix 1](#) Schedule of Activities

).

The bypassing agents that are currently used for treating patients with hemophilia A are associated with specific side effects, such as thromboembolic events, hypersensitivity reactions, myocardial infarction, and disseminated intravascular coagulation (Bui et al. 2002; Dentali et al. 2011; Tjønnfjord 2004; Wójcik et al. 2009). In addition, these agents are administered according to a frequent dosing schedule, which may reduce patient compliance thereby making these regimens less effective and compromising their cost-benefit ratio (Thornburg 2010). Therefore, there currently exists an unmet need to develop novel therapeutics for use in hemophilia A patients with inhibitors. This study will provide long-term safety data on the prophylactic use of emicizumab.

### **3.3.9 Rationale for Interim Analyses**

*Owing to the long-term nature of this study, interim analyses will be conducted in order to obtain accurate information on the safety, efficacy, immunogenicity, and PK of prophylactic emicizumab at specific points throughout the study.* The first interim analysis will be performed once approximately 100 patients have received treatment with emicizumab for at least 24 weeks. A second interim analysis will be performed when approximately 100 patients have received treatment with emicizumab for at least 52 weeks. The data from these analyses will subsequently be presented to the iDMC in order to enable them to effectively monitor the study.

### **3.3.10 Rationale for Patient-reported Outcome (PRO) Assessments**

During the study, electronic capture of HRQoL, health status (EQ-5D-5L) will be obtained using an ePRO device. *Patient preference data (EmiPref) will be collected on paper forms.*

HRQoL is an important outcome in the care of patients with hemophilia (Brown et al. 2009). HRQoL in hemophilic patients is multifaceted and is affected by disease symptoms (e.g., pain, bleeding), treatment (prophylactic, on demand, side effects), limitations on daily functioning, anxiety / depression, and time spent in hospital.

The goal of measuring HRQoL is to quantify any treatment benefits from the patient perspective. Previous studies that have used the *Hemophilia Quality of Life questionnaire* (Haemo-QoL), a measure of HRQoL parameters affected by hemophilia in children and adolescents, have reported improvements in physical health, feelings, view of self, family relations, friend relations, perceived support, relation with others, participation in sports, dealing with hemophilia, views of treatment, views of the future, and relationships (Santagostino et al. 2014). Improvements in physical health, feelings, view of self, and participation in work have also been observed on the adult version of the measure, the Haem-A-QoL (Stasyshyn et al. 2014).

The HRQoL measures employed in the current study will be used to investigate the impact of prophylactic administration of emicizumab in adolescents and adults with hemophilia A. In addition, the measures will be used to evaluate the longitudinal changes in HRQoL with emicizumab compared with the previous treatment regimen that the patients received.

The EQ-5D-5L is a standardized, preference-based measure of generic health status that is applicable to a wide range of health conditions and treatments. It measures five dimensions

of health: mobility, ability to self-care, ability to undertake usual activities, pain / discomfort, and anxiety / depression. The EQ-5D-5L also assesses current overall health. The goal of measuring EQ-5D-5L is to assess the impact of treatment with emicizumab over time on overall health and the different health dimensions. Data from the EQ-5D-5L can also be used to inform pharmacoeconomic evaluations.

The study will also evaluate patient preference for treatment (EmiPref). Previous studies have noted that patients express preference for treatments that do not have negative effects (e.g., pain that results from infusions), are not time-consuming, are not associated with high treatment burden, and have a goal of achieving a “normal life” (Cimino et al. 2014). The inclusion of a fit-for-purpose preference survey after the completion of 3 months of emicizumab treatment will provide information on whether SC emicizumab is preferred to the previous treatment and explore the potential underlying reasons for any findings. This assessment will be performed after 3 months as the patients will have gained sufficient experience with emicizumab and SC injection, while still being reliably able to recall their experience with their prior therapy.

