aPCCs may be associated with side effects, such as thromboembolic events, hypersensitivity reactions, myocardial infarction, and disseminated intravascular coagulation (Bui et al. 2002; Dentali et al. 2011; Tjønnfjord 2004; Wójcik et al. 2009). Both aPCC and rFVIIa are administered intravenously, with aPCC prophylaxis requiring every other day dosing and rFVIIa requiring daily (or more frequent) dosing.

The development of effective prophylactic treatment options with less frequent dosing requirements is a high, unmet medical need in the population of patients with hemophilia A with FVIII inhibitors. Reducing the time and burden associated with frequent IV dosing and the impact of the disease on aspects of physical health and other areas of functioning and well-being, while promoting increased efficacy, may further improve HRQoL. This hypothesis is supported by a study in which patients receiving a prophylactic treatment with FEIBA had improved HRQoL than those who received episodic therapy (i.e., administered following bleeds) with FEIBA (Gringeri et al. 2013). Therefore, despite major therapeutic advances in the treatment of hemophilia A, opportunities still remain to optimize and transform therapy, in particular for patients with inhibitors.

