**Table 8 Objectives and Corresponding Endpoints**

Objectives	Corresponding Endpoints
Primary Objective:	

 
To evaluate the overall safety and tolerability of prophylactic administration of emicizumab
 
	
 
Incidence and severity of all adverse events, including thromboembolic events, microangiopathic hemolytic anemia or TMA (e.g. hemolytic uremic syndrome), systemic hypersensitivity, anaphylaxis, and anaphylactoid events
 
Changes in physical examination findings, vital signs, and laboratory parameters
 

Secondary Objective:	

 
To evaluate the efficacy of prophylactic administration of emicizumab
 
	
 
To evaluate the efficacy of prophylactic administration of emicizumab on the basis of the number of bleeds over time
 
To evaluate the HRQoL of patients according to Haem-A-QoL (<math>\geq 18</math> y) or Haemo-QoL-SF (ages 12–17) scores over time
 
To evaluate the health status of patients according to EQ-5D-5L scores over time
 
To assess patient preference for the emicizumab regimen compared with the previous regimen used
 

Immunogenicity Objective:	

 
To evaluate the immunogenicity of emicizumab
 
	
 
To assess the incidence and clinical significance of anti-emicizumab antibodies
 

PK Objective:	

 
To obtain emicizumab PK data
 
	
 
To obtain PK data for emicizumab at defined timepoints
 

[figure not shown]
EQ-5D-5L=EuroQoL Five-Dimension-Five Levels Questionnaire; Haem-A-QoL=Hemophilia Adult Quality of Life Questionnaire; Haemo-QoL-SF=Hemophilia Quality of Life Short Form; HRQoL=Health-Related Quality of Life; PK=pharmacokinetic; TMA=thrombotic microangiopathy

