#### **4.6.2 HRQoL (Haem-A-QoL and Haemo-QoL-SF)**

As different HRQoL measures (Haem-A-QoL and the Haemo-QoL-SF) will be used for adult and adolescent patients, all calculations and analyses will be conducted separately for each patient population.

The number and percentage of patients who complete the Haem–A–QoL or Haemo-QoL-SF will be summarized at each scheduled time point. The compliance rate will be plotted over time. The compliance rate is based on the total number of patients expected to complete the questionnaire at a particular time point – i.e., those patients who had the opportunity to complete the scale. The number of expected questionnaires is calculated using the time windows of scheduled visits defined in the protocol. The analysis period used will overlap with the corresponding efficacy period, as the start will be the start of the efficacy period and the end will be either then end of the efficacy period or will be extended to the last entry on the device, for the last efficacy period of a subject, if it occurred later.

Total score and domain sub-scales at each visit for the Haem-A-QoL and Haemo-QoL-SF will be calculated and summarized descriptively. The corresponding mean along with its 95%CI plots will be provided.

The change from baseline to 6 months as well as for each of the post-baseline time points in the total score for each questionnaire will be analyzed by the paired t-test.

The proportion of patients who report changes that exceed clinically meaningful thresholds will be reported. A clinically meaningful threshold is defined as a decrease of 7 points in the Haem-A-QoL total score (Wyrwich et al., 2015), 5 points in the Haemo-QoL-SF total score (Santagostino et al., 2014) and 10 points for physical health.

A descriptive summary of each of the scale will be produced, in which the domain score at each visit and the associated change from baseline will be summarized. Paired t-tests will be performed on the change from baseline to 6months for the scales.

Note: before calculation the scale and total score, several items need to be reverse scored. The reverse scoring for those items is as follows: (1=5), (2=4), (3=3), (4=2), and (5=1). Any (0) will be recoded as missing data for the purposes of scale scoring. For details see Appendix 3: HRQoL QUESTIONNAIRES

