#### **4.6.4 Patient preference**

Summary statistics on patient preference for the emicizumab regimen compared with the previous regimen used will be presented.

Preference survey, which is administered to patients at Month 3, consists in main questions:

- the first question is related to the treatment preference with 3 possible responses: (a) older hemophilia IV treatment prior to enrollment in the study; (b) new study drug SC emicizumab treatment; (c) no treatment preference.
- the second question, only asked to patients with a preference (responses a or b at first question), is related to factors influencing treatment preference (14 possible factors). For each factor, the patient should tick whether the factor is important and, if yes, provide an importance rank for the top 3 factors ("1" being the most important, "2" the second most important and "3" the third most important)

The number and percentage of patients who complete the Preference survey will be summarized.

Proportion of patients preferring the older hemophilia treatment, emicizumab, or without treatment preference will be computed along with 95% CIs (using the Pearson–Clopper one sample binomial method).

This defines two sub-populations of the "All patient population":

- The PREFSC population, which includes all the patients that responded: "Prefer the new study treatment (SC)"
- The PREFIV population, which includes all the patients that responded: "Prefer my old hemophilia treatment (IV)"

For patients who have a preference to either emicizumab or the old IV hemophilia treatment, the factors influencing the preference can be treated like ordered categorical variables as follow:

- Category 1 = “Most important”, when factor was ranked first among top factors
- Category 2 = “2nd most important”, when factor was ranked second among top factors
- Category 3 = “3rd most important”, when factor was ranked third among top factors
- Category 4 = “Influenced preference but not most important”, when factor was ticked but not ranked among top factors
- Category 5 = “Did not influence preference”, when factor was not ticked as important

Summaries of these categories will be produced by factor for the PREFSC and the PREFIV populations. Bar charts showing proportions of patient within each preference factors will also be produced for the PREFSC and the PREFIV populations:

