#### **4.6.7 Subgroup Analyses**

Descriptive summaries of both treated bleeds and all bleeds will be produced on the subgroups presented below. The summaries will include subgroup model based ABR (95% CI) and calculated mean ABR (95% CI).

The pre-specified subgroups are:

- Age at baseline:  $< 18, \geq 18$
- Age at baseline:  $< 65, \geq 65$
- Race: Asian, Black or African American, White, Other
- Number of bleeds during 24 weeks prior to study entry:  $< 9, \geq 9$
- Number of target joints at baseline: no target joint, any target joint
- Hemophilia severity: mild, moderate, severe
- Previous treatment regimen: prior episodic, prior prophylactic (in case a subject have history of both prior episodic and prior prophylactic treatments, he will be considered as prophylactic)

Additional region- and/or country-specific analyses may be performed to support regulatory submission as needed.

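### HRQoL change and treatment preference are set against each patient's previous regimen, but the SAP reports them with prior episodic and prior prophylactic patients pooled

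*Protocol*

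**What the plan says.** **Aim.** For HRQoL, Protocol 3.3.10 states that "the measures will be used to evaluate the longitudinal changes in HRQoL with emicizumab compared with the previous treatment regimen that the patients received". For preference, the endpoint in Protocol Table 8 reads "To assess patient preference for the emicizumab regimen compared with the previous regimen used". EQ-5D-5L has a different goal, also in 3.3.10: "The goal of measuring EQ-5D-5L is to assess the impact of treatment with emicizumab over time on overall health".

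**Who is enrolled.** Protocol 3.3.2: "Patients may have received episodic or prophylactic treatment before enrollment". No planned shares are given. Protocol 1.1 cites a study in which "patients receiving a prophylactic treatment with FEIBA had improved HRQoL than those who received episodic therapy".

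**Analysis.** SAP 4.1 takes the Week 1 questionnaire as the PRO baseline. Under SAP 4.6.2, "The change from baseline to 6 months as well as for each of the post-baseline time points in the total score for each questionnaire" is analysed by paired t-test, and the proportion of patients passing a responder threshold is reported. The only split is adults versus adolescents, who use different questionnaires. SAP 4.6.3 handles EQ-5D-5L without a split. In SAP 4.6.4, "Proportion of patients preferring the older hemophilia treatment, emicizumab, or without treatment preference will be computed along with 95% CIs"; the reasons are then tabulated by which treatment was preferred.

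**Subgroups.** SAP 4.6.7 opens: "Descriptive summaries of both treated bleeds and all bleeds will be produced on the subgroups presented below". Its list includes prior episodic versus prior prophylactic treatment, with patients who have both histories classed as prophylactic. No patient-reported outcome is covered.

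**The concern.** The two admitted regimens are different comparators. For a patient treated on demand, the change from Week 1 reflects moving from episodic treatment to weekly SC prophylaxis. For a patient already on IV prophylaxis, it reflects replacing one prophylactic treatment with another. The protocol's own background expects HRQoL to differ between episodic and prophylactic treatment, so Week 1 need not represent the same state in the two groups.

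A pooled mean, responder proportion or preference proportion averages the two contrasts with weights set by who happens to enrol. A reader with only the pooled row cannot tell whether patients already on prophylaxis felt better, or whether they preferred the new treatment. EmiPref does not help by itself: it refers to the old IV treatment without recording whether that was on-demand or prophylactic. Only a link to the baseline history can separate the groups.

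**Working it through.** **1. Plan's own figures.** The only design calculation is the adverse-event precision table (SAP 2.3). It reproduces with Clopper-Pearson limits at N = 200: 5 events 0.8–5.7%, 10 events 2.4–9.0%, 20 events 6.2–15.0%, 30 events 10.4–20.7%. It says nothing about HRQoL or preference, for which no precision is stated.

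**2. Inputs from the documents.** Protocol 1.2.2.3 gives Haem-A-QoL physical-health results at Week 25 in adults of the earlier randomised trial, all previously treated on demand. The adjusted means are 54.2 without prophylaxis (n = 14) and 32.6 on emicizumab (n = 25); lower is better. The difference is 54.2 − 32.6 = 21.6, 95% CI 7.9 to 35.2. That trial had 53 + 7 = 60 prior episodic and 49 prior prophylactic patients of 109, so 45% prior prophylaxis.

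**3. Assumptions.** The between-arm difference stands in for a within-patient gain in prior on-demand patients. Prior-prophylaxis patients gain zero. The prior-prophylaxis share p is unknown and is varied from 20% to 80%.

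**4. Pooled mean gain** = (1 − p) × g, where g is the gain in prior on-demand patients:

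| p | g = 7.9 | g = 21.6 | g = 35.2 |
|---|---|---|---|
| 20% | 6.32 | 17.28 | 28.16 |
| 50% | 3.95 | 10.80 | 17.60 |
| 80% | 1.58 | 4.32 | 7.04 |

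At the earlier trial's mix with g = 21.6: 60/109 × 21.6 = 11.9. The effect within each group is fixed down every column; only the mix changes.

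**5. Responders.** The 10-point physical-health threshold in SAP 4.6.2 applies to individual patients. Assume normally distributed changes with SD 20. This SD is back-calculated from the CI above: half-width 13.65, SE about 6.7, SE ÷ √(1/25 + 1/14) ≈ 20. The proportion above threshold is then Φ((21.6 − 10)/20) = 72% in prior on-demand patients and Φ(−10/20) = 31% in prior-prophylaxis patients with no mean gain. Pooled, (1 − p) × 72% + p × 31% runs from 64% at p = 20% to 39% at p = 80%.

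**6. Preference.** Suppose all prior on-demand patients and half of prior-prophylaxis patients prefer SC. The pooled proportion is (1 − p) × 100% + p × 50%: 90%, 75% and 60% at p = 20%, 50% and 80%.

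**7. Precision after a split.** The 95% CI half-width for a mean change is t × SD/√n. At SD 20 it is 2.8 points pooled (n = 200), 4.0 in each stratum at 100/100, and 6.4 and 3.1 at 40/160. For preference, 50/100 has a 95% CI of 40–60% and 20/40 one of 34–66%. These n are upper bounds: Haem-A-QoL is for adults only, and some forms will be missing.

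**The case against.** The strongest reply is that the stated comparison is already made. Each patient's on-treatment score is set against their own Week 1 score, which reflects the regimen they came from, and each EmiPref answer weighs that patient's own old treatment against the new one. The endpoint table describes HRQoL simply as scores over time, and nowhere do the documents promise results by type of previous regimen. All analyses are descriptive, and SAP 4.4 tabulates prior episodic and prophylactic treatment, so readers can see the mix. This stands as far as it goes: the pooled change is a valid average. It does not remove the point, because knowing the mix does not reveal the effect in each group, and a descriptive estimate still needs an identifiable comparator.

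Four stronger readings are tempting and should not be drawn:

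- A reader might infer that the pooled gain is wholly an effect of starting prophylaxis. That needs zero gain in prior-prophylaxis patients, for whom the documents give no HRQoL result. Protocol 1.2.2.3 reports 79% fewer treated bleeds than on previous bypassing-agent prophylaxis, which argues against zero.
- A reader might describe the on-demand contrast as prophylaxis versus nothing. Inclusion criterion 5 requires documented treatment within six months, so it is prophylaxis versus episodic treatment.
- A reader might count EQ-5D-5L as a missed comparison too. Its stated goal is impact over time.
- A reader might treat a pooled mean above 10 points as meeting the SAP's criterion. That figure is a per-patient responder threshold and has no standing for a mean.

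Missing preference answers from patients who stop before Month 3 are partly visible, since completion and discontinuation are both summarised.

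**Conclusion.** The gap is real and modest. HRQoL change and preference are both framed against the previous regimen, two different previous regimens are admitted, and no patient-reported outcome is reported by regimen, although the SAP has the variable and uses it for bleeds. The pooled rows are valid averages but do not answer the question for either group.

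The size can only be illustrated. Under a 21.6-point gain in one group and none in the other, the pooled physical-health mean moves between 17.3 and 4.3 points purely with the enrolment mix; with 7.9 or 35.2 in place of 21.6 the ranges are 6.3 to 1.6 and 28.2 to 7.0. This rests on the assumed zero gain, on using a between-arm difference as a within-patient change, and on an unknown mix. A real gain in prior-prophylaxis patients would narrow the range. The preference range of 90% to 60% is likewise hypothetical. The illustration shows sensitivity to the mix; it does not predict the result.

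**What to change.** In SAP 4.6.7, extend the existing prior-regimen subgroup to:

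- the Haem-A-QoL and Haemo-QoL-SF change-from-baseline and responder tables (SAP 4.6.2);
- the EmiPref proportions (SAP 4.6.4);
- the EQ-5D-5L tables (SAP 4.6.3), labelled as an aid to interpretation.

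Keep the pooled rows. Base any statement that sets emicizumab against what patients took before on the two strata. Footnote that patients with both histories are classed as prophylactic, so that stratum includes some on-demand experience. Optionally, show EmiPref non-completers as separate rows, with those who stopped before Month 3 distinguished from those who simply did not return the form.

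The cost is SAP wording and extra rows in tables already planned; the variable is collected and its derivation is defined, so no patients, visits or data are added. The downside is wider intervals per stratum and adolescent strata that may be too small for more than a listing or simple counts.
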